4.1 Screening and Enrollment Visit

At screening and enrollment (to be conducted remotely using the Way2Health platform), eligibility will be ensured and informed consent will be taken. Upon completion of the informed consent and screening survey questions (Appendix III), the Way2Health platform will automatically create a unique study ID. Individuals not wanting to take part in the study will be provided with a form to return should they wish to decline to take part in the trial. This will ask for basic demographic information and their reasons for declining, including an option to give a reason if they prefer not to. At study entry all participants will be given a brief training via the PSOM-secure Zoom video-based platform on how to use the Way to Health application after downloading onto their smartphone. Participants will be provided with details regarding how to

Study Protocol: Supporting Self-Management of Healthy Behaviors (SMART-HABITS)

contact the research team via email or phone at any time if they subsequently wish to withdraw from the study. This contact information will remain easily accessible via the participants' individual Way to Health web portal dashboards throughout the study.

Participants will mailed an OMRON 5 series wireless blood pressure cuff (BP7250) or if preferred by the participant, given the OMRON blood pressure machine at one of the nephrology practices using appropriate social distancing and face coverings. The blood pressure monitor given to each participant will be checked for accuracy. Participants will be directed to a brief training video on how to correctly measure their blood pressure using this device. Participants will also be mailed a physical activity sensor watch (Fitbit Inspire 2) that will monitor their step counts, or if preferred by the participant, they will be given the Fitbit at one of the nephrology practices using appropriate social distancing and with face coverings. The participants will be asked to wear the Fitbit every day for the entire 12 weeks. All participants will be asked to authorize the electronic transmission of de-identified data to the study database from the devices during the Way2Health enrollment phase.

Instructions on how to correctly set up both wireless devices will also be mailed and available online as a google doc (see Appendix II).

Participants will be asked to complete baseline questionnaires and report on their sociodemographic characteristics, including age, gender, highest level of education, and race/ethnicity, baseline step counts on their smartphone or on a computer. They will also be asked to fill out an action plan for their BP and daily step count goals. The intervention will commence after these baseline measures have been collected.

At the end of the study, qualitative interviews will be scheduled with willing participants to provide an in-depth understanding of the factors that may facilitate or diminish the acceptability of the intervention and adherence to the implementation. Open-ended inductive questions will be used to elicit user perspectives and experiences of the intervention, allowing participants to freely describe their experiences and views in their own way. Interviews will be audio-recorded, fully transcribed and analyzed thematically.

4.4. Subject Completion/Withdrawal

Participants will be withdrawn from the study if they become no longer eligible to participate (e.g., no longer can walk or self-monitor BP). Participants who choose not to continue with the study will be offered the opportunity to continue self-monitoring only rather than withdrawing completely from the study and asked if they would be willing to be interviewed for additional feedback.

5. Study Evaluation and Measurements

5.1 Screening and monitoring Evaluations and Measurements

A screening mean blood pressure measurement of $\leq 180/100$ mmHg using historical blood pressures documented in the electronic medical record is required for enrollment. Additional measurements include the remote transmission of BP monitoring and daily step counts. Questionnaires listed below will collect patient reported measures.

5.2 Efficacy Evaluations

The efficacy measures in this trial are only secondary or exploratory as the study's purpose is to assess feasibility. The study was not powered to detect efficacy or effectiveness. The evaluations of effectiveness will include questionnaire scores, BP measures and step counts at baseline, 4, 8 and 12 weeks. Questionnaires will be administered at baseline, 4 weeks, 8 weeks, and end of the study (after 12 weeks).

5.3 Feasibility Evaluations

To assess feasibility, we will collect information on participant retention rates, usage of the SMART-HABITS application, transmitted blood pressure and step count data, usability surveys, and conduct semi-structured interviews to assess user-experience.

6. Statistical Considerations

Since this is a feasibility study, there are no true primary endpoints for statistical consideration.

Study Protocol: Supporting Self-Management of Healthy Behaviors (SMART-HABITS)

6.1 Primary Endpoints

The RE-AIM framework, which focuses on five dimensions (reach, effectiveness, adoption, implementation and maintenance), considered to be important for behavioral health interventions will guide the evaluation for the primary endpoints of feasibility of the SMART-HABITS program.

- 1) Adoption: a) participant retention rate at 4, 8, and 12 weeks, b) Percentage of participants who used SMART-HABITS at any point during the 12 weeks.
- 2) Adherence: a) percentage of self-monitored BP transmissions performed out of the recommended and b) percentage of step count data transmissions out of the recommended.
- 3) Acceptability: a) improvement of the pre- and post-study scores on the attitudes toward mHealth questionnaire, b) satisfactory ratings on the ease of use survey during the study and at the end of the study and, c) interview feedback after the end of the pilot study.

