- 2) **Developing Goals and Action plan:** setting personalized goals for blood pressure self-monitoring and physical activity
 - Patients will complete a patient-generated “action plan” to assist in developing goals to help them initiate changes and achieve success in managing their condition effectively
 - Develop goals for blood pressure control by the end of the study and the level of adherence to blood pressure measurements
 - Develop daily step count goal for physical activity over the study period
- 3) **Support Adherence and Increase Self-efficacy:**
 - Provide personalized daily and weekly texts to encourage participation and progress towards blood pressure monitoring, physical activity goals
 - For blood pressure readings that are texted to the Way to Health platform, the participant will receive predefined comment on the control of their blood pressure
 - For each daily step count transmission, the participant will also receive similar feedback
 - Additionally, if the participant elects to enroll an accountability sponsor, progress will be shared with this individual
- 4) **Monitoring:**
 - For the participants using the OMRON Connect app, self-monitoring will be captured by electronically recording blood pressure measurements via Bluetooth by participant using a wireless blood pressure device (OMRON 5 series cuff)
 - CKD patients will be asked to self-measure blood pressure using a blood pressure cuff at home at least 3 times per week and then further personalized by goal-setting
 - Remote monitoring of physical activity will be done via a physical activity sensor (Fitbit Inspire 2) that is worn as a watch and link the data to the Fitbit app in order to help patients monitor their own personal progress.
- 5) **Social Support:** support through kin/sponsor
 - As indicated above in supporting adherence, by sharing feedback and progress with family members, peers or any other identified sponsor/support aims to support adherence.
 - In addition, there will be a link provided to the available social support:
 - Peers Lending Support- free, anonymous phone calls with other CKD patients (<http://www.kidney.org/patients/peers/index.cfm>)
 - Participants will also be provided with directions to access friends and a community with the FitBit App.
 -

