discussing CKD on social media.^{137,138} CKD patients have reported they desire social support¹³⁹ but are unsure of available support and wish that SMS programs included information about local, community-based resources, organizations and support groups.¹⁴⁰

2. Study Aims and Research Questions

The primary aim is to assess the feasibility of using a smartphone-based behavioral intervention, SMART-HABITS, to support self-management of individuals with pre-dialysis CKD patients.

Research Questions:

- Will patients with CKD adopt SMART-HABITS?
- Will patients with CKD adhere to prompts of the SMART-HABITS intervention?
- Will patients with CKD wear and use wearable remote sensors (i.e. wireless blood pressure cuff and physical activity sensor)?
- How many patients with CKD will drop out throughout the study period?
- Is SMART-HABITS acceptable to patients?
- What are patient views and experiences of using SMART-HABITS?
- Is there any change in blood pressure control throughout the study period?
- How well did participants achieve their step count goals throughout the study period?
- Did SMART-HABITS associate with improved self-efficacy, knowledge, attitudes to mHealth, self-management, or quality of life?

Study Protocol: Supporting Self-Management of Healthy Behaviors (SMART-HABITS)

3. Investigational Plan

A cross-over prospective trial of feasibility of a smartphone-based behavioral intervention in a real-life setting.

General Schema of Study Design

Nephrology Practices: PCAM and Presbyterian

Identification of Potential Participants(48-72 weeks):

- Letter of invitation sent by research team after reviewing schedule for follow up visits, followed by phone call
- Study advertisement posters within the practice
- Pre-Screen all eligible patients who respond to invitation or inquire about poster

Conducted remotely through Way to Health: Baseline consultation and enrollment:

- Screening survey: Assess eligibility
- Informed Consent
- self-reported height, weight
- Patients given unique log-in for Way to Health
- Patients provided with instructions with how to use wearable devices (BP cuff and FitBit)
- Provide authorization for data to be shared from wearable devices
- Complete survey questions

Intervention (12 weeks)

- Arm 1 (first 6 weeks): Text message reminders to check BP and text BP readings to research team
 - o Tailored text message feedback for transmitted BP readings

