6.3 Statistical Methods

We will describe the study population with mean values (standard deviations) or medians and quartiles as appropriate for continuous variables and percentages for categorical variables using STATA software. Specifically, we will report the enrollment rate, the retention rate, and participant ratings on ease of use surveys. We will explore if these characteristics differ by age, gender, and education level with analysis of variance and Pearson's Chi2-testing. We will report the adoption as the percentage of participant still enrolled in the intervention at 4, 8, and 12 weeks and the percentage of participants who used SMART-HABITS at any point during the 12 weeks of the pilot trial. We will report the percentage of the self-monitored BP transmissions performed out of the recommended and also the percentage of the step count data transmissions out the recommended during the pilot trial.

We will perform an exploratory analysis of the change in 1) pre- and post-trial questionnaire scores, and 2) baseline BP and first week mean step count compared to the mean BP and step counts after 4, 8, and 12 weeks using paired t-tests, recognizing that over time the amount of information will diminish as we anticipate fall out, but also, a longer time for the intervention to have an effect. We will explore the association of baseline questionnaire scores with adoption and adherence with linear regression models adjusted for age, sex, race, and education. These will be exploratory analyses since the study was not powered to detect a statistically significant difference. We hypothesize that higher adherence and adoption will be associated with increased scores on baseline measures of self-efficacy, attitude toward mHealth, and self-management. We will also explore for trends in adherence with generalized linear mixed effects models and if blood pressure control or amount of steps modifies trend in adherence.

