7.1 Description

The intervention will utilize the Way to Health platform to provide: a) text message reminders, b) text message tailored feedback in response to transmitted data on blood pressure (in the text message arm) and daily step counts, c) positive affirmation text messages sent throughout the study to encourage behavior participation, d) provide links to educational resources, including a video on demonstrating how to correctly perform blood pressure self-mentoring in the portal, e) provide links to community resources and CKD patient forums within the portal, and the f) option to select a accountability partner to share the participant's reminders and feedback. The intervention was developed using a theory-based, and evidence-based approach.

Study Protocol: Supporting Self-Management of Healthy Behaviors (SMART-HABITS)

The Way to Health platform is an automated information technology platform that integrates wireless devices, clinical trial randomization and enrollment processes, messaging (text, e-mail, voice), self-administered surveys, and secure data capture for research purposes.^{141,142} Way to Health has been used in prior behavior intervention studies.¹⁴³⁻¹⁴⁶

At enrollment, a questionnaire (see Appendix IV) will be completed by all participants to capture demographics, kidney disease knowledge, ability to manage kidney disease, confidence in managing kidney disease, opinions of and ability to use mobile health technology. At enrollment, participants will complete a patient-generated “action plan” (questions in Appendix IV) in order to set realistic goals and encourage participants to create goals that involve positive action- with the minimum targets. Participants will develop short-term goals to help initiate changes and achieve success.

Participants will be asked to check their BP at least three times per week and then to communicate these BP readings with the research team using text message or with the OMRON Connect app (depending on the phase- please see below), and upon receipt, the participants will then receive tailored feedback.

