Participants will be asked to set a daily step goal of at least 3,000 steps per day at the start of the study and transmit their step count information to the research team on a daily basis. By providing a minimum threshold puts more emphasis on encouraging more sedentary individuals to walk more and less emphasis on getting highly active individuals to be more active. Participants will be reminded once a day in the evening to sync their steps with the FitBit app in order to transmit them to the Way to Health platform. Participants will receive daily individual performance feedback on their steps from the previous day. Participants will later be sent messages to see if they would like to increase their daily step goal.

Participants will be instructed how to correctly undertake BP self-monitoring to promote self-efficacy through a demonstration video available on Way to Health. Participants will be asked to rehearse self-monitoring at the initial study visit via a secure video-based platform using Zoom.

- Phase 1 (weeks 1-6):
 - After consenting to participate in the study, participants will be randomized to start with Texting (Arm 1) or the OMRON Connect App (Arm 2) to communicate BP readings.
 - Each arm will receive specific instructions pertinent to the specific phase tasks - available as a google document and will also be mailed at the beginning of the study (Appendix II).
 - Participants randomized to the texting arm in Phase 1 will receive automated text message reminders to check their BP on a personalized basis (minimum of three days per which) as participants will choose which days and times to receive these reminders at the beginning of the study. Participants will then transmit the BP readings with text message to the secure Way to Health server. If a blood pressure reading is not received within 3 hours, another reminder will be sent. Automated text message feedback will be sent after the BP reading is recorded with a tailored message regarding any further required actions based upon the BP readings obtained. Any participant with a single systolic blood pressure reading >200mmHg or two consecutive systolic blood pressure readings >180 mmHg or diastolic blood pressure readings >110 mmHg will be contacted immediately by an MD ([name]) for assessment (including evaluation for symptoms of hypertensive emergency) and referral to the emergency department, if indicated. Please see full text message algorithm (Appendix VII).

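### Could the BP adherence percentage read 100% while half the participants miss the weekly minimum?

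*Combined protocol and SAP*

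**What the plan says.** Section 6.1 lists adherence among the primary feasibility endpoints and defines its blood-pressure part as the "percentage of self-monitored BP transmissions performed out of the recommended". Section 6.3 restates it: "We will report the percentage of the self-monitored BP transmissions performed out of the recommended". Neither section says whether surplus readings count, or whether the percentage is pooled or taken per participant or per week. Section 6.3 also makes adherence the outcome of exploratory regressions on baseline scores, and adds: "We will also explore for trends in adherence with generalized linear mixed effects models".

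The recommendation itself is a minimum. Section 7.1 states: "Participants will be asked to check their BP at least three times per week". Section 1.2 has readings taken "at home at least 3 times per week and then further personalized by goal-setting".

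Other parts of the protocol bear on what the ratio means. Section 2 asks: "Will patients with CKD adhere to prompts of the SMART-HABITS intervention". In the texting phase (Section 7.1) reminders go out to "check their BP on a personalized basis (minimum of three days per which" (the last word is evidently a slip for week), on days the participant picks. Section 7.1 continues: "If a blood pressure reading is not received within 3 hours, another reminder will be sent". App users also choose their reminder days. The schema in Section 3 promises weekly feedback on BP-monitoring adherence, and Section 7.1 starts a re-engagement procedure after more than a week without a reading.

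**The concern.** A percentage of a minimum has no natural ceiling. If the numerator is every reading sent and the denominator is three per week, a keen participant's extra readings make up for another participant's missing ones, and a busy week makes up for an empty one. The reported figure could then show full adherence when half the participants, or half the weeks, fall below what was asked.

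A personal-goal denominator has a different weakness: the same behaviour scores lower for someone who set a more ambitious goal. Adherence answers one of the study's stated questions and feeds the exploratory models, so an inflated figure could make the intervention look more feasible than it was.

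**Working it through.** **Inputs.** 40 participants (Section 3.3.1), 12 weeks (Section 3.3.2), minimum three readings a week (Sections 1.2 and 7.1). The plan states no adherence figure or target, so there is nothing to reproduce. All transmission rates below are assumptions.

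Denominator at the minimum: 40 × 12 × 3 = 1,440 readings, or 36 per participant and 120 per week over the whole group.

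**1. Uncapped total over three per week, against a weekly cap of three.**

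| Assumed pattern | Uncapped | Capped weekly at 3 | Minimum met |
|---|---|---|---|
| 20 send 5/week, 20 send 1/week | (100 + 20)/120 = 100% | (60 + 20)/120 = 67% | 20/40 = 50% of participants |
| 20 send 4/week, 20 send 2/week | (80 + 40)/120 = 100% | (60 + 40)/120 = 83% | 20/40 = 50% of participants |
| One person alternating 5 and 1 | (6×5 + 6×1)/36 = 100% | (6×3 + 6×1)/36 = 67% | 6/12 = 50% of weeks |

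The offset is therefore real under this reading.

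**2. Dependence on the assumed rates.** Keep the second group at 1/week and let the first send 3, 4, 6 or 7. The uncapped figure is 80, 100, 140 or 160 over 120, that is 67%, 83%, 117% or 133%; the capped figure stays at 67%. At 3/week the two agree. A reading of exactly 100% needs surplus and shortfall to cancel.

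**3. The part-of-whole reading.** Count each recommended or prompted reading as done or not done, and take the 5/1 pattern.
- Three prompts each: (60 + 20)/120 = 67%, the same as the cap.
- Five prompts in the first group and three in the second: (100 + 20)/(100 + 60) = 75% pooled, or (100% + 33.3%)/2 = 67% averaged over participants.
- Five prompts for all: 120/200 = 60%.

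None of these can exceed 100%, and no surplus offsets a shortfall.

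**4. Would the low group go unnoticed?** One reading a week, evenly spaced, leaves gaps of exactly 7 days, on the edge of the re-engagement rule. If the day varies, the gap between consecutive weeks' readings is 7 + (later day − earlier day), which exceeds 7 whenever the day moves later in the week. With a random day in each of 12 weeks (assumption), a participant has no gap over 7 days only if the day never moves later: C(18,6)/7^12 = 18,564/13,841,287,201, about 1 in 750,000. Practically everyone in that group would meet the trigger.

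**5. Would the inflation be visible?** The regressions in Section 6.3 need one value per participant. The 5/1 pattern gives 5/3 = 167% and 1/3 = 33%. A value of 167% would prompt a query. The mixed models for trend need repeated values over time, so alternating weeks need not stay hidden either.

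**6. What a cap would cost.** Score each week as min(days with a reading, 3)/3, with reading-days per week X ~ Binomial(7, m/7), where m is the mean.

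| m | E[min(X,3)]/3 | P(X ≥ 3) |
|---|---|---|
| 3 | 83% | 64% |
| 4 | 95% | 87% |
| 5 | 99% | 98% |

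A person who averages exactly the minimum is scored at 83% through ordinary week-to-week variation alone.

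**The case for a change.** The strongest case for a change is that, in a feasibility study with no formal sample size (Section 6.4), the descriptive figure is itself the result. Sections 6.1 and 6.3 do not adopt the part-of-whole reading in so many words, and the 5/1 pattern can yield anything from 60% to 100% across the readings above. Half is not the worst case: 8 participants at 7/week and 32 at 2/week give (56 + 64)/120 = 100% with 80% below the minimum, and two evenly spaced readings a week would not trigger re-engagement. Prompt-based denominators vary with the reminders each person chose, and the documents do not say whether the app's reminder schedule is recorded. Settling the definition before data are seen would take one paragraph.

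What stands is that the definition is unwritten, so a report of this endpoint has to state its denominator and unit. What does not stand is that the plan is likely to mislead. No passage calls for the uncapped total. A higher frequency would usually come from a personalised goal, which may raise the recommendation along with the count. The promised weekly feedback implies a working rule, and Appendices IV and VII, which hold the action plan and message algorithm, are not in the text available here; a definition there cannot be excluded.

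**Conclusion.** The concern does not call for a change. The uncapped ratio can read 100% with half the participants below the minimum, but only on a reading that the text permits and nothing in it adopts. On the ordinary reading, supported by the research question about prompts and by the follow-up of unanswered text reminders, the measure is bounded and the offset does not arise.

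The size of any overstatement cannot be estimated from the documents: the contrasts of 100% with 67% or 83% rest wholly on assumed transmission rates. The consequence is also limited. Section 6 opens by saying that a feasibility study has no true primary endpoints in the statistical sense, and no test, threshold or go/no-go rule depends on the figure. Only a descriptive percentage and exploratory models are touched.

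The natural replacement, a weekly cap at three reading-days, is a trade-off on which statisticians can reasonably differ. It sets aside the personalised goals of Section 1.2, counts days where the recommendation is in times per week, and scores a participant averaging exactly three days at 83%. This is missing detail that analysts would probably fill sensibly.

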 - Participants randomized in Phase 1 to the OMRON Connect App arm will complete the same survey questions as those in the Texting Arm. Participants using the OMRON connect app will also receive reminder messages on a similar frequency as the texting arm and will also be customized the participant's schedule as they can choose which days and times to receive push notification reminders delivered by the OMRON connect app. Upon receipt of the BP reading, participants will receive similar BP feedback (Appendix VII).
- Phase 2 (weeks 7-12):
 - At the conclusion of week 6, individuals will “crossover” to the opposite study arm and will continue in the study for an additional 6 weeks using the opposite technology to communicate their BP readings.

Motivating and positive affirmation messages will be sent to participants on a weekly basis (Appendix VII). After 4 weeks,

Study Protocol: Supporting Self-Management of Healthy Behaviors (SMART-HABITS)

and 8 weeks of the intervention, a usability survey (Appendix V) will be sent out to assess the ease of use of SMART-HABITS. Automated messages will be sent at key milestones to promote adherence to study procedures. Weekly feedback will be sent the morning after the end of the week. Daily feedback on performance from the prior day will be sent each morning.

Within SMART-HABITS' smartphone web-based application, there will be a portal which provides:

- Educational information that incorporates both clinical and lay-experiential CKD knowledge: Educational resources will present the health-related benefits of self-monitoring, reducing blood pressure, and increasing physical activity. Positive expectations will be outlined by ways that use self-monitoring BP and increasing physical activity may reduce the chances of experiencing negative health consequences.
- Graphical displays of personally set goals and real-time progress to goals
- Web links to social support

Throughout the study, if participants are identified to have low engagement with the intervention, identified through remote monitoring and defined as no BP readings for >1 week or no step counts in 4 days, they will undergo a re-engagement protocol. The re-engagement protocol includes the research team contacting participants with text messages to re-engage them and if after two attempts, the participant continues to not be engaged, they will be called and interviewed over the phone to provide more granular information to assess real-time barriers.

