9.2 Data Collection and Management

Questionnaires will be completed electronically through the Way to Health Platform on the SMART-HABITS app on a participant's smartphone or on a computer at enrollment (Appendix IV) and at the end of study (Appendix VI).

Questionnaires include:

1. Measure of CKD Knowledge: Kidney Knowledge Survey (KiKS)¹⁴⁷
2. Measure of e-health literacy: eHealth Literacy scale (eHEALS)- an eight-item measure of eHealth literacy developed to measure individuals' combined knowledge and perceived skills at finding, evaluating, and applying electronic health information to health problems.¹⁴⁸
3. Measure of chronic disease self-efficacy: Self-efficacy for Managing Chronic Disease Scale (SEMCDS)- 6 item scale.¹⁴⁹
4. Self-management in Chronic Disease: Partners in health scale^{150,151}
5. Kidney Disease Quality of Life (KDQOL-36)¹⁵², consists of five subscales:
 - o 1- Physical component summary (12 items about general health, activity limits, ability to accomplish desired tasks)
 - o 2 -Mental component summary (12 items depression and anxiety, energy level, and social activities)
 - o 3- Burden of kidney disease (4 items on how much kidney disease interferes with daily life, takes up time, causes frustration, or makes the respondent feel like a burden)
 - o 4- Symptoms and problems (12 items about how much respondent bothered by CKD related symptoms)
 - o 5- Effects of Kidney Disease on Daily life (7 items about much how respondent bothered by fluid limits, diet restrictions, ability to work around the house or travel, feeling dependent on doctors or other medical staff, stress or worries, sex life and personal appearance).

Several questions from the Attitudes toward mHealth and remote monitoring (10 item questionnaire).⁶⁹

Data collected from participants' smartphone using Fitbit app and OMRON Connect ap, including survey and questionnaire responses and will be sent electronically to the Way to Health research platform and stored on a secure data server. This system is hosted onsite at the University of Pennsylvania with a level of security identical to that used for the clinical data of patients within the University of Pennsylvania Health System.

Study Protocol: Supporting Self-Management of Healthy Behaviors (SMART-HABITS)

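### No scored questionnaire is sent at withdrawal, so the primary attitudes score covers completers only and the ease-of-use ratings miss early leavers and everything after exit

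*Combined protocol and SAP*

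**What the plan says.** Section 6.1 gives Acceptability three components:

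- (a) a change score, given as "improvement of the pre- and post-study scores on the attitudes toward mHealth questionnaire"
- (b) a usability measure scored at several times, given as "satisfactory ratings on the ease of use survey during the study and at the end of the study"
- (c) a qualitative part, given as "interview feedback after the end of the pilot study"

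For (b), Section 7.1 says that after 4 weeks "and 8 weeks of the intervention, a usability survey (Appendix V) will be sent out to assess the ease of use of SMART-HABITS". Section 6.3 compares pre- and post-trial questionnaire scores with paired t-tests. It expects attrition but names no missing-data method and no denominator for the ease-of-use ratings.

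Under Section 4.4, people who stop are offered self-monitoring alone as an alternative to leaving completely, and are "asked if they would be willing to be interviewed for additional feedback". No section sends the attitudes items or the ease-of-use survey at that moment. Under Section 7.1, participants who stay disengaged after two text attempts are contacted by telephone: "they will be called and interviewed over the phone to provide more granular information to assess real-time barriers". Section 9.5 samples 5–10 participants for interview, deliberately including low engagers, and plans further enrolment if loss to follow-up reaches 20%.

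The sections disagree on questionnaire timing. Section 5.2 and the consent section (numbered 8.6) have questionnaires at baseline, weeks 4 and 8, and the end. Section 9.2 lists enrolment and end of study only.

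**The concern.** Leaving a self-management programme can itself be a sign that the participant did not find it acceptable. If scores come mainly from those who stay, the result answers a narrower question than the one in Section 2, which asks whether the programme is acceptable to patients. The study could then report high satisfaction partly because less satisfied participants had gone.

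Retention is reported separately under Adoption. It shows how many left, not what they thought. The protocol values such information elsewhere: Section 4.1 gives people who decline enrolment a form asking why, yet people who tried the programme and left receive no scored form. Ratings not requested at exit generally cannot be recovered later, so this has to be settled in advance.

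**Working it through.** The plan gives no acceptability rate, cut-off or sample-size calculation, so there is no figure of its own to reproduce.

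**Who is scored, by time of exit**

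| Exit | (a) Pre/post attitudes | (b) Ease of use |
|---|---|---|
| Before week 4 | none | none |
| Weeks 4–8 | no post-study value | week 4 possible |
| Weeks 8–12 | no post-study value | weeks 4 and 8 possible |
| Completes | yes | all |

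If attitudes items are also given at weeks 4 and 8 (Sections 5.2 and 8.6), later leavers have an interim attitudes score. The endpoint as worded does not use it.

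**Inputs.** N = 40 (Section 3.3.1). Loss d = 20% is the trigger in Section 9.5, giving 8 leavers and 32 completers; 10% and 30% are sensitivity values. Satisfaction of 90% in stayers and s = 0–50% in leavers is assumed.

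**Case 1: component (b), week-12 completers only.** Overstatement = d × (0.90 − s).

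- d = 10%: 0.10 × 0.40 to 0.10 × 0.90 = 4 to 9 points
- d = 20%: 0.20 × 0.40 to 0.20 × 0.90 = 8 to 18 points
- d = 30%: 0.30 × 0.40 to 0.30 × 0.90 = 12 to 27 points

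With 80% of stayers satisfied, the 20% row becomes 0.20 × 0.30 to 0.20 × 0.80 = 6 to 16 points.

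**Case 2: component (b), last available rating used.** Assume exits are uniform over 12 weeks, every survey sent is answered, and a leaver's early rating reflects the view held at exit. Then 8 × 4/12 = 2.67 leavers are unrated and 5.33 are rated, so 37.33 people have a rating.

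- s = 0: reported 28.8/37.33 = 77.1%; all enrolled 28.8/40 = 72.0%; difference 5.1 points
- s = 50%: reported (28.8 + 2.67)/37.33 = 84.3%; all enrolled (28.8 + 4)/40 = 82.0%; difference 2.3 points

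**Bounds without assuming leavers' views.** If 26 of 32 completers are satisfied (81%) and the 8 leavers are unrated, the figure for all 40 lies between 26/40 = 65% and 34/40 = 85%.

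**Does replacement help?** Enrolling 50 at 20% loss gives 40 completers. The overstatement in Case 1 is still 0.20 × (0.90 − s), because it depends on the share lost and the gap, not on the number of completers.

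**Component (a).** The percentages above do not apply to a change score. If mean change differed by 0.5–1.0 SD between stayers and leavers (assumed), the bias at 20% loss would be 0.20 × 0.5 to 0.20 × 1.0 = 0.10 to 0.20 SD.

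**The case against.** A reader might infer that leavers vanish from Acceptability altogether. The documents do not support that. Leavers after week 4 or week 8 can already have ease-of-use ratings. Interview feedback is itself component (c), leavers are asked for an interview, disengaged participants are phoned, and low engagers are sampled on purpose. Those who move to self-monitoring only have not fully withdrawn, and nothing says their questionnaires stop. What remains is that the interviews are optional and unscored, so they cannot repair (a) or (b). The plan also does not say that interviews with leavers count toward (c), which is worded as feedback after the pilot ends.

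A reader might also take 8–18 points as the expected bias. That range treats every leaver as unrated. It falls to about 2–5 points once earlier ratings are used, although the plan does not say they will be.

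Nor do the documents show that leavers are less satisfied. Section 4.4 includes withdrawal for lost eligibility, such as no longer being able to walk, which says nothing about acceptability.

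Finally, Section 6 says there are no true primary endpoints for statistical consideration, and no acceptability threshold or go/no-go rule is given. That limits the consequence. It does not remove the need, in a feasibility study, to be clear about who was scored. The paired-test gap is also part of a general missing-data question that affects BP and steps; the exit survey is the part specific to this point. The appendices could not be checked.

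**Conclusion.** The point holds in a limited form. As written, component (a) is completer-only. Component (b) misses those who leave before week 4 and all later ratings from those who leave afterwards. Otherwise leavers' views enter only through optional, unscored interviews, and enrolling more patients at 20% loss does not change this.

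The direction, an overstatement of acceptability, rests on the assumption that leavers are less satisfied. On the illustrative rates at 20% loss, the size for the ease-of-use percentage is 8–18 points if only week-12 completers count. It is about 2–5 points if week-4 and week-8 ratings are carried in and exits are uniform. This is a cheap, optional improvement, not a flaw that undermines the study.

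**What to change.** - **Section 4.4:** have Way to Health send the existing ease-of-use survey and attitudes items at withdrawal, as an optional request. State that participants who move to self-monitoring only keep receiving the scheduled questionnaires.
- **Sections 6.1 and 6.3:** report the number rated and the number satisfied out of all enrolled, using the last available rating including any exit rating. Put the completer figure beside it. Add a sensitivity lower bound that counts unrated participants as not satisfied. For the attitudes score, state how many enrolled participants contribute a pair.
- **Sections 5.2, 9.2 and 8.6:** reconcile whether questionnaires are given at weeks 4 and 8, and say which ones.

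The cost is one automated message using instruments already in the study, on a platform that already runs self-administered surveys (Section 7.1), plus a few extra figures in the results. Some leavers will not respond, and the headline figure may be less favourable. Last available rating is one reasonable choice among several; stating the number rated out of all enrolled is the minimum.
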